8.0		Evaluation at Termination of Protocol	25
9.0		Response Criteria and Toxicity Assessment	26
10.0		Criteria for Discontinuing Therapy	27
11.0		Statistical Parameters	28
12.0		Protocol Management and Data Collection	28
13.0		Reporting Requirements	29
14.0		Protocol Amendments	33
15.0		References	33
Appe	ndices:	•	
	A:	Performance Status Criteria	36
	B:	Adverse Drug Reaction Report Form	37
	C:	NCI Common Toxicity Criteria	40
	D:	Angiogenic Markers: sample collection/storage/methodology	41
	E:	Informed Consent Form (under separate cover)	42
	F:	Risk of Fetal Exposure, Pregnancy Testing Guidelines & Acceptal	ole
:		Birth Control Methods	43
	G.	REVLIMID® Education and Counseling Guidance Document	45
	H.	Lenalidomide Information Sheet	48
	I:	RevAssist® for Study Participants.(RASP)	51
	J	FDA-approved REVLIMID® PPAF Example	52

.

1.0 PROTOCOL ABSTRACT:

١

PHASE II TRIAL OF REVLIMID® (LENALIDOMIDE) FOR THERAPY OF RADIOIODINE-UNRESPONSIVE PAPILLARY AND FOLLICULAR THYROID CARCINOMAS

1.1 Key Personnel:

1.1.1 Principal Investigator:

[name].

Thyroid Oncology, Division of Hematology/Oncology

Department of Internal Medicine

University of Kentucky Medical Center

[contact]

[contact]

Email:

[contact]

1.1.2 Co-Investigators:

[name].

Department of Diagnostic Radiology

University of Pittsburgh

- Objectives: Primary objectives are to assess the anti-tumor activity of REVLIMID® (lenalidomide), administered as a single agent, in patients with distantly metastatic thyroid carcinomas which are unresponsive to systemic radioiodine, in terms of tumor response and response duration. Secondary objectives are: 1) to assess differences in the primary objectives between papillary and follicular thyroid carcinomas, 2) to assess treatment toxicities and duration of toxic effects, and 3) to determine if parameters of angiogenesis: serum levels of vascular endothelial growth factor (VEGF-A), soluble VEGF receptors (sVEGF-1 & sVEGF-2), and thrombospondin-1, change in response to treatment and correlate with primary objectives.

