1.8.3... Extended Therapy phase: Lenalidomide (Revlimid®) will be provided to research subjects for the duration the extened phase participation in this trial at no charge to them or their insurance providers. Lenalidomide will be provided in accordance with the RevAssist® program. Per standard RevAssist® requirements all physicians who prescribe lenalidomide for research subjects enrolled into this trial, and all research subjects enrolled into this trial, must be registered in and must comply with all requirements of Celgene's RevAssist® program. Prescriptions must be filled within 7 days. Only enough lenalidomide for one cycle of therapy will be supplied to the patient each cycle.

Patients will have a CBC prior to each new cycle of Revlimid®. Standard-of-care clinical visits with the principal investigator will take place every 3 months as long as the patient is participating in the Extended Therapy phase.

1.9 Response Criteria:

- 1.9.1 Complete Response (CR): Disappearance of all radiological and clinical evidence of tumor. The patient must be free of all tumor related symptoms for at least 4 weeks.
- 1.9.2 Partial Response (PR): 30% or greater decrease in the sum of the longest diameter of all measured lesions (or alternatively, ≥30% reduction of calculated tumor volumes) for at least 4 weeks.
- 1.9.3 Minor Response (MR): For tumors with a documented rate of progression (calculated as either the linear slope of calculated tumor volumes vs. time for the immediate year prior to initiating this study or as the slope of the logarithm of tumor volumes vs. time over the same interval), a decrease in the rate of progression by ≥50%.
- 1.9.4 Stable Disease (SD): No change or <30% decrease in the tumor volume (calculated as in 1.9.2) for at least 4 weeks.
- 1.9.5 Progressive disease (PD): Less than a 50% reduction in the rate of progression (see 1.9.3), an increase of >25% in the size of any measured lesion, or the appearance of new metastatic lesions.

Table 1: Schedule of Study Assessments

	Screening	Cycle	Cycle	Cycle	Cycle	Cycle	Cycle	Cycle	Cycle ,	Cycle	Cycle	ಲ	Cycle 12	Extension Phase	Extension Phase:	Extended Therapy
Procedure	prior to initiating	. H	79	т	খ	ŧn	9	r-	\$	٥,	2	Ħ	or Endin		Every 1 month	Phase: Every 3
	therapy												g Study			months
Complete medical history (prior treatment),	×															
Physical examination Kamofsky (clinic visit)	×	×	×	×	×	×	×	×	×	×	×	×	×			×

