5.0 Investigational Plan

5.1 Patient Eligibility:

5.1.1 Inclusion Criteria:

- 1) Histological confirmation of follicular, papillary, insular, or Hürthle-cell thyroid carcinoma. Histologic slides and/or tissue blocks must have been reviewed at the University of Kentucky Medical Center.
- 2) Patients must have progressive, unresectable, distantly metastatic tumor, which does not concentrate radioactive iodine. Alternatively, follicular or papillary thyroid carcinoma patients with distant tumor burdens which have not sufficiently responded to more than 800 mCi I-131 cumulative therapy and are progressive (criteria #4) may be appropriate for inclusion.
 - 3) No systemic chemotherapy agents within 4 weeks of initiation of therapy.
- 4) Patients must have 2 consecutive radiographic evaluations demonstrating a cumulative 30% increase in tumor volume over a time period of one year or less.
- 5) Patient must be over the age of 18 years with the ability to understand and willing to sign an informed consent.
- 6) Females of childbearing potential (FCBP)[†] must have a negative serum or urine pregnancy test with a sensitivity of at least 50 mIU/mL within 10 14 days prior to and again within 24 hours of starting lenalidomide and must either commit to continued abstinence from heterosexual intercourse or begin TWO acceptable methods of birth

control, one highly effective method and one additional effective method AT THE SAME TIME, at least 28 days before she starts taking lenalidomide. FCBP must also agree to ongoing pregnancy testing. Men must agree to use a latex condom during sexual contact with a FCBP even if they have had a successful vasectomy. All patients must be counseled at a minimum of every 28 days about pregnancy precautions and risks of fetal exposure. See Appendix F: Risks of Fetal Exposure, Pregnancy Testing Guidelines and Acceptable Birth Control Methods, AND also Appendix G: Education and Counseling Guidance Document.

- 7) Karnofsky performance status ≥70 %.
- 8) Baseline Laboratory Studies: Absolute neutrophil count (ANC) >1000/mm³; platelet count \geq 100 K/mm³; Creatinine \leq 2 mg/dL, and transaminase levels (AST/SGOT, ALT/SGPT) \leq 2 x ULN (or \leq 5 x ULN if hepatic metastases are present).
- 9) Disease free of other prior malignancies for ≥ 5 years, with the exception of currently treated basal cell/squamous cell carcinoma of the skin or "in-situ" carcinoma of the cervix or breast.

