MR images will be obtained utilizing 3D volume acquisition techniques because of the non-rectangular pulses on 2D axial images, which require a 1 mm gap between slices to reduce cross talk. Because of the 1 mm gap, inaccuracies in total volume will be introduced on the 2D techniques. All MR scans will be performed on either a 1.5 T superconductive magnet Siemen's Vision or Symphony scanner. Use of gadolinium contrast agent may be used depending on the imaging findings.

Choice of CT or MR will depend on patient cooperation. Although MR is far superior to CT in discriminating tissue types, the 3D volume technique requires that the patient be able to hold completely still for at least 8-10 minutes, whereas each CT scan slice can be obtained in less than 1 second. It is anticipated that the majority of imaging studies will be CT scans. If outside CT or MR scans are of sufficient resolution and the scanning factors are known, the hard copy scans can be digitized and thus transferred to the work station. If these are t adequate, then repeat scans will be performed at this institution. Follow up scan monitoring therapy will be reviewed for tumor volume changes, morphological changes in size, and presence of bony/cartilage invasion.

- 6.3 Angiogenic Markers (see Appendix E for sample collection/storage/methodology)
 - 6.3.1 Proangiogenic cytokine: vascular endothelial growth factor-alpha (VEGF-A).
 - 6.3.2 Antiangiogenic factors: soluble VEGF receptor-1 (sVEGFR-1), sVEGFR-2, and thrombospondin-1 (TSP-1).
- 6.4 Toxicity Monitoring: Please refer to Table 1: Schedule of Study Assessments
 - 6. 4.1 Hematologic: CBC with differential/platelet count.
 - 6. 4.2 Biochemical: Serum comprehensive metabolic profile
 - 6. 4.3 Pregnancy prevention: Pregnancy tests must occur within 10 14 days and again within 24 hours prior to initiation of lenalidomide. FCBP with regular or no menstruation must have a pregnancy test weekly for the first 4 weeks and then every 28 days while on therapy (including breaks in therapy); at discontinuation of lenalidomide and at 30 Days +/- 2 days post the last dose of lenalidomide.

Females with irregular menstruation must have a pregnancy test weekly for the first 4 weeks and then every 14 days while on therapy (including breaks in therapy), at discontinuation of lenalidomide and at Day 14 and Day 28 post the last dose of lenalidomide (see Appendix F: Risks of Fetal Exposure, Pregnancy Testing Guidelines and Acceptable Birth Control Methods):

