- 8.1.2 Radiological Studies: CT (without contrast for lung, otherwise with contra &/or MRI of evaluable disease.

8.2 Angiogenic Markers:

- 8.2.1 Proangiogenic cytokine: VEGF-A.
- 8.2.2 Antiangiogenic factors: sVEGFR-1, sVEGFR-2, and TSP-1.
- Evaluations during "Extended Therapy" phase: The following studies are obtained after the one-year protocol has concluded and the patient is maintaining a clinical response to REVLIMID® therapy and elects to continue to receive this drug and may receive REVLIMID through the RevAssist program. Note that these studies are performed as "standard-of-care" assessments that are appropriate for oncologic follow-up:
 - 8.3.1 Tumor Assessment (obtained at physician visits every 3 months):

 Tumor markers: Thyroglobulin Panel (TG & anti-TG Ab), TSH, free T4.

 Angiogenic Markers: Not done.

 Radiological Studies: CT (without contrast for lung; otherwise with contrast) of evaluable disease.

 Additional standard assessments: biochemistry panel and physical examination.
 - 8.3.2 Toxicity Monitoring (obtained every month while taking REVLIMID®): CL with differential/platelet count, and pregnancy test every 4 weeks if regular menstruation and every 2 weeks if irregular. All patients must continue to follow the birth control guidelines.
- 9.0 Response Criteria and Toxicity Assessment: Overall responses will be assessed as described in Figure 4, below. These assessments are adapted from RECIST Criteria (referenced in Fig. 4).

9.1 Parameters of Response:

- 9.1.1 Complete Response (CR): Disappearance of all radiological and clinical evidence of tumor. The patient must be free of all tumor related symptoms for at least 4 weeks.
- 9.1.2 Partial Response (PR): 30% or greater decrease in the sum of the longest diameter of all measured lesions (or alternatively, ≥30% reduction of calculated tumor volumes) for at least 4 weeks.
- 9.1.3 Minor Response (MR): For tumors with a documented rate of progression (calculated as either the linear slope of calculated tumor volumes vs. time for the immediate year prior to initiating this study or as the slope of the logarithm of CONFIDENTIAL

tumor volumes vs. time over the same interval), a decrease in the rate of progression by ≥50%.

- 9.1.4 Stable Disease (SD): No change or <30% decrease in the tumor volume (calculated as in 9.1.2) for at least 4 weeks.

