- 9.1.5 Progressive disease (PD): Less than a 50% reduction in the rate of progression (see 9.1.3), an increase of >20% in the size of target lesions, or the appearance of new metastatic lesions.

Figure 4. Overall responses for all possible combinations of tumor responses in target and non-target lesions with or without the appearance of new lesions* (Adapted from Therasse P, Arbuck SG, Eisenhauer EA, Wanders J, Kaplan RS, Rubinstein L, Verweij J, Van Glabbeke M, van Oosterom AT, Christian MC, Gwyther SG 2000 New guidelines to evaluate the response to treatment in solid tumors. European Organization for Research and Treatment of Cancer, National Cancer Institute of the United States, National Cancer Institute of Canada. J Natl Cancer Inst 92:205-16)

Target lesions	Non-target lesions	New lesions	Overall response
CR.	CR	No	CR
CR.	Incomplete response/MR/SD	No	PR
PR.	Non-PD	No	PR.
MR	Non-PD	No	MR
SD	Non-PD	No	SD
PD	Any	Yes or no	PD
	PD	Yes or no	PD
Any Any	Any	Yes	PD + 1.1a disease

^{*}CR= complete response; PR= partial response; MR= minor response; SD= stable disease; and PD= progressive disease.

9.2 Toxicity Assessment: This will be performed at intervals defined in section 7.0 using criteria defined in appendices A, B, & C.

10.0 Criteria for Discontinuing Therapy:

- 10.1 Progressive Disease is an indication to discontinue therapy.
- Adverse event(s) that, in the judgment of the Investigator, may cause severe or permanent harm or which rule out continuation of the study drug.
- 10.3 Non-compliance by the patient with protocol requirements.
- 10.4 Patient desire to discontinue therapy.
- 10.5 Evidence of pregnancy.

- 10.6 ... Withdrawal of consent.
- 10.7 Lost to follow-up.
- 10.8 Death

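### Partial response can be met by a 30% fall in summed diameters or a 30% fall in volume, which are different depths of shrinkage, so PR and any CR+PR rate mix the two

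*Combined protocol and SAP*

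**What the plan says.** Section 9.1.2 sets PR at "30% or greater decrease in the sum of the longest diameter of all measured lesions (or alternatively, ≥30% reduction of calculated tumor volumes"), and section 1.9.2 in the abstract has the same alternative: "or alternatively, ≥30% reduction of calculated tumor volumes) for at least 4 weeks". Stable disease (SD) in section 9.1.4 is "No change or <30% decrease in the tumor volume (calculated as in 9.1.2) for at least 4 weeks". Minor response (MR) in section 9.1.3 is a cut of at least 50% in the rate of progression, calculated from tumor volumes.

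Section 9.0 says of the criteria: "These assessments are adapted from RECIST Criteria (referenced in Fig. 4"). Figure 4 keeps the categories apart: "PR= partial response; MR= minor response; SD= stable disease". The primary objective is anti-tumor activity "in terms of tumor response and response duration".

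Volume is the working scale elsewhere. Entry (section 5.1.1, item 4) needs two evaluations "demonstrating a cumulative 30% increase in tumor volume over a time period of one year or less". Section 6.2.3 describes volume tracing and adds "Follow up scan monitoring therapy will be reviewed for tumor volume changes, morphological changes in size, and presence of bony/cartilage invasion"; it gives no procedure for diameters. Section 11.0 plans a 95% confidence interval for the response rate in up to 25 patients and does not say which categories make a responder.

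**The concern.** The text treats a 30% fall on a length scale and a 30% fall on a volume scale as interchangeable. Volume depends on three axes, so the volume route is usually much easier to meet. A lesion that shrinks 12% along every axis is a PR by volume and 18 points short of one by diameter.

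At stake is what PR means in the primary objective. A reader told that the criteria derive from RECIST will take PR as shrinkage of roughly that depth, when an 11% to 16% diameter fall may have been enough. The PR/MR split is affected whatever a responder turns out to be. So is any CR+PR rate with its interval, and so are the dates from which PR duration is counted. Section 6.2.3 and the footnote to Table 1 make volumetry the described method, so the easier route will normally be available.

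**Working it through.** The plan gives no figure for the effect of the scale, so there is none to reproduce. The inputs are the two 30% thresholds (9.1.2), scans every two 28-day cycles (7.1.2, Table 1) and N=25 (11.0).

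**1. One lesion, or lesions shrinking in proportion.** Volume is proportional to the product of three axes.

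| Axes shrinking equally | Diameter fall equal to a 30% volume fall | Volume fall equal to a 30% diameter fall |
|---|---|---|
| Three | 1 − 0.7^(1/3) = 11.2% | 1 − 0.7³ = 65.7% |
| Two | 1 − 0.7^(1/2) = 16.3% | 1 − 0.7² = 51.0% |
| Longest only | 30% | 30% |

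For the 12% example: 1 − 0.88³ = 31.9% of volume.

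**2. Several lesions of different sizes (illustrative spheres).** Section 9.1.2 sums over all measured lesions, so the table above sets no limits for a patient.

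- One 40 mm lesion falls to 34 mm and five 10 mm lesions are stable. Diameter sum 90 to 84, down 6.7%. Volume in units of d³: 69,000 to 44,304, down 35.8%. This is PR by volume only.
- One 40 mm lesion is stable and three 20 mm lesions fall to 5 mm. Diameter sum 100 to 55, down 45%. Volume 88,000 to 64,375, down 26.8%. This is PR by diameter, yet it fits the volume wording of SD in 9.1.4.

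**3. Direction.** Under either/or, every diameter responder still counts. The PR count can therefore only equal or exceed the diameter-only count, and a patient's first qualifying scan can only be the same or earlier.

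**4. Where the added patients would otherwise go.** Entry requires growth, so the pre-treatment slope is positive. Net volume shrinkage cuts that slope by more than 100%, which meets the 50% needed for MR. They do not fit SD, because their volume fall is at least 30%.

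**5. Size for a CR+PR rate.** Each such patient adds 1/25 = 4.0 points. As an illustration, assume 2 CR+PR by diameter; intervals are exact (Clopper-Pearson).

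| Added by volume only | CR+PR | Rate (95% CI) |
|---|---|---|
| 0 | 2/25 | 8.0% (1.0 to 26.0) |
| 1 | 3/25 | 12.0% (2.5 to 31.2) |
| 3 | 5/25 | 20.0% (6.8 to 40.7) |
| 5 | 7/25 | 28.0% (12.1 to 49.4) |

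**6. Onset.** As an illustration, assume a constant volume fall r per scan interval, with three axes shrinking equally. The first qualifying scan is ceil(ln(threshold)/ln(1 − r)), with threshold 0.7 for volume and 0.7³ = 0.343 for diameter.

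- r = 10%: 3.39 and 10.16, so cycle 8 by volume and not within 12 cycles by diameter.
- r = 20%: 1.60 and 4.80, so cycle 4 against cycle 10, a gap of 24 weeks.
- r = 40%: 0.70 and 2.09, so cycle 2 against cycle 6, a gap of 16 weeks.
- r = 50%: 0.51 and 1.54, so cycle 2 against cycle 4, a gap of 8 weeks.
- r = 65.7% or more: no gap.

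**The case against.** The strongest reply is that volume is a deliberate and suitable scale here. Entry, MR and the imaging method all use it, and the criteria claim only to be adapted from RECIST. That stands: the fault is not the use of volume but one category with two unequal thresholds.

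A reader might go further and infer that the plan leaves PR undecided when the scales disagree. The text does not support this for a patient who qualifies by volume alone. The wording reads most plainly as either/or, and SD is written in terms of tumor volume, so that patient is a PR. The reverse case in step 2 is less tidy, since it meets both the PR and the SD wording.

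A reader might also treat 11.2% to 30% as a fixed band of discordance. It holds for one lesion or proportional shrinkage; over several lesions the discordance can start lower or change direction.

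The effect on the planned analysis is conditional. Section 11.0 does not define a responder, and section 3.3 describes response in the earlier thalidomide trial as running from PR down to disease stabilization. If MR or SD counts, the overall rate and the stage-1 decision do not move. Nor do the documents say how many patients will be discordant, so the counts in step 5 show scale and are not a forecast.

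**Conclusion.** The point holds as a problem of non-equivalence. Following 9.1.2 as written puts two depths of response into one category of the primary objective. Relative to a diameter criterion it can only add PRs and date them the same or earlier. The addition is 4.0 points of CR+PR per patient who is PR by volume alone at N=25, and zero if there are none. The 11.2%/16.3% and 65.7%/51.0% equivalents assume a single lesion or proportional shrinkage.

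Two stronger conclusions a reader might draw are not supported. One is that the overall response rate and the stage-1 rule are inflated: that needs responder to mean CR+PR. The other is that mean PR duration is lengthened. Earlier onset lengthens it, but added shallow responders may progress sooner. For example, two PRs of 8 cycles joined by two of 4 cycles give a mean of (8+8+4+4)/4 = 6, not 8.

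**What to change.** Name one governing scale for PR in 1.9.2 and 9.1.2, and put the SD boundary in 1.9.4 and 9.1.4 on the same scale. Either choice works:

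- **Diameter:** PR is a fall of at least 30% in the summed longest diameters for at least four weeks, with the volume alternative deleted.
- **Volume:** keep the scale that entry, MR and section 6.2.3 use. If RECIST-comparable depth is intended, raise the cut-off to about 65% and state the three-axis assumption. A 65% volume fall is a diameter fall of 1 − 0.35^(1/3) = 29.5% with three axes but 1 − 0.35^(1/2) = 40.8% with two, where the matching cut-off would be 51.0%.

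Report the other scale as a separate prespecified secondary measure, including volume reduction of at least 30% and its duration. State that MR takes precedence over SD when both fit. This matters most under the diameter choice, where a patient with a diameter fall below 30% and a shrinking volume would meet both.

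The cost is wording in four places, the precedence sentence and one secondary measure. No new imaging is needed, but there is some extra diameter reading, which 9.1.2 already implies. The downside is fewer and later PRs and, if diameter is chosen, PR and SD on one scale with MR on another.
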